13.8 Exclusion criteria. Subjects will not be eligible to participate in the study if any of the following criteria are met: 1) a desire to not participate; 2) children with severe renal impairment will be excluded from the study; 3) post-pubertal females who are pregnant or unwilling to use highly-effective methods to prevent pregnancy will be excluded from the study; 4) breast-feeding females will be excluded from this study; and 5) subjects who have an allergy to miglustat or any of the components within the drug product will be excluded from this study.

13.9 Exit/discontinuation criteria. Subjects will exit the study if any of the following conditions exist: 1) subject voluntarily withdraws from the study; 2) subject acquires any of the listed exclusion criteria; 3) subject develops severe renal impairment; 4) subject becomes pregnant; or subject's well-being, in the opinion of the Investigator, would be compromised by study continuation.

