16.0 Subject Withdrawal

16.1 How to withdraw subjects. Patients can choose to withdraw from the study at any time. We will request that the patients notify the investigators if they wish to withdraw from the study. Subjects will stop the study if:

- 1) The subject voluntarily chooses to withdraw from the study.
- 2) The study investigator(s) may choose to discontinue patient from study if patient is experiencing adverse effects that cannot be managed by dose adjustments of the study agent.

16.2 Data collection and follow-up for withdrawn subjects. Patients will continue to receive full clinical services in our lysosomal disease treatment clinic.

16.3 Subject compensation. There will be no compensation to subjects for participation in this clinical trial.

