18.0 Data Analysis

18.1 Subject populations for analysis:

- Intention-to-treat Population (ITT): All subjects who initiate any portion of the treatment regimen in association with this study
- Per-protocol Population (PP): Includes all subjects who initiate treatment and are compliant with at least 75% of prescribed drug doses of miglustat, and at least 3:1 ketogenic diet.
- Safety population: All subjects who receive any amount of the combination treatment regimen. Due to the nature of a combination treatment, multiple groups may be identified, should partial adherence be observed.

18.2 Sample size determination. The sample size for the study was determined primarily by feasibility due to the extremely rare nature of the disease. There are two distinct sub-types to be evaluated: infantile and juvenile. Analysis will be based on variability estimates from published natural history studies^{8,11,19} of the infantile form and juvenile form, and correlation between baseline and annual follow-up for up to 4 years.

18.3 Statistical analysis. Descriptive analyses of baseline characteristics and outcomes will include means, standard deviations, medians, and ranges for continuous variables and frequencies for categorical variables. Treatment compliance for each group will also be evaluated. All analyses will be conducted separately for the two disease sub-types – infantile and juvenile – due to the highly heterogeneous patient groups.

The primary analysis for Syner-G treatment regimen will use the intention-to-treat (ITT) population and evaluate overall survival. This will be evaluated based on chronological age at time of death or conclusion of study (whichever occurs first), and compared to available natural history data. Median survival will be compared to previously reported natural history studies of infantile⁹ and juvenile¹¹ forms. Infantile median survival was estimated at 47 months based on data from the National Tay-Sachs and Allied Diseases database for patients born after 2000.⁹ Median survival for the juvenile form was estimated at 14.5 years.¹¹

A secondary endpoint will be the rate of change (i.e., slope) in neurocognitive functioning over the duration of follow-up, compared to available natural history data. This analysis will be conducted separately for each of the two sub-types: infantile and juvenile. The primary

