21.0 Study Discontinuation

21.1 Discontinuation rules. The NIH and the University of Minnesota IRB have the authority to stop or suspend this study at any time. Additionally, the following study discontinuation rules apply:

- 1) That the rate of severe adverse events is such that continued participation would compromise subject safety.
- 2) Target subject accrual has not met, and cannot meet trial objectives.

21.2 Participant discontinuation. All data acquired prior to termination for the reasons outlined below will be included in the primary analysis unless patient withdraws consent. Every effort will be made to conduct a final study visit with the participant, and participants will be followed clinically until, if applicable, all adverse events resolve. Participant discontinuation in this study will occur for the following reasons:

- Participants who develop kidney function problems while in this study will be withdrawn from this study.
- Females who are able to become pregnant, and who are sexually active, must use a highly effective birth-control method to prevent pregnancy while in this study. If a participant becomes pregnant while in this study, they will be withdrawn from this study.
- If a patient develops bleeding due to low platelets while in this study, treatment with miglustat will be stopped.
- If a patient develops severe diarrhea and/or weight loss that cannot be managed by changing the ketogenic diet formula or lowering the miglustat dose, the patient will be removed from the study.
- Withdrawal of consent
- Withdrawal by the participant
- Withdrawal of the participant by the Investigator(s) (If a subject experiences an adverse effect from the treatment medication, dose reduction adjustments will be made to the medication, or the subject will be withdrawn from the study, if indicated.)

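### Children removed for unmanageable diarrhoea or weight loss leave the study with no planned vital-status follow-up, so the primary survival analysis may be censored by toxicity

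*Combined protocol and SAP*

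**What the plan says.** Section 21.2 lists reasons for participant discontinuation. On severe diarrhoea or weight loss, the rule is that if it "cannot be managed by changing the ketogenic diet formula or lowering the miglustat dose, the patient will be removed from the study"; the consequence is exit from the study. The bullet just before it, on bleeding from low platelets, only stops miglustat. The protocol therefore already separates stopping treatment from leaving the study, but not for this toxicity.

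On data after exit, the plan says:

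- **21.2, data kept:** "All data acquired prior to termination for the reasons outlined below will be included in the primary analysis unless patient withdraws consent".
- **21.2, follow-up:** a final visit is attempted, and "participants will be followed clinically until, if applicable, all adverse events resolve".
- **16.2**, whose heading covers data collection and follow-up of withdrawn subjects, has one sentence: "Patients will continue to receive full clinical services in our lysosomal disease treatment clinic". It names no data item.
- **16.1** adds a broader discretionary exit: investigators "may choose to discontinue patient from study if patient is experiencing adverse effects that cannot be managed by dose adjustments of the study agent".
- **13.9** opens its own list of exits with "Subjects will exit the study if any of the following conditions exist" and has no follow-up provision.
- **13.1** plans telephone contact with families and health care providers, but for children who miss an annual visit and are not withdrawn.

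Section 18.1 defines the ITT set as "All subjects who initiate any portion of the treatment regimen in association with this study". Section 18.3 evaluates survival in that set by age at death or at the end of the study, and compares the median with 47 months (infantile) and 14.5 years (juvenile).

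**The concern.** A child removed under 21.2 has started the regimen and so remains in the ITT set. The endpoint needs that child's status at death or at study end, but the plan stops short of obtaining it. Survival after exit may then be unknown, and the natural handling is censoring at exit.

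Censoring is harmless when its cause is unrelated to the risk of death. Here the cause is severe toxicity, including uncontrolled weight loss, in children with a fatal neurodegenerative disease. If these children are at higher risk, the remaining risk set looks healthier than the treated group really is and estimated survival is too high. In a single-arm comparison with a fixed historical median, nothing offsets this.

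The trigger is not remote. Section 20.1 names diarrhoea and weight loss as the most common miglustat side effects in children with these diseases. The same gap applies to the other exits in 13.9, 16.1 and 21.2.

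**Working it through.** **1. Could another section fill the gap?** The documents state no power, event count or dropout rate, so there is no figure to reproduce. Reading the relevant sections together:

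| Section | What it covers | Survival after exit? |
|---|---|---|
| 21.2 | Pre-termination data; attempted final visit; clinical follow-up until adverse events resolve | No |
| 16.2 | Continued clinic care | No data named |
| 13.1 | Telephone contact for missed visits | Only children not withdrawn |
| 18.3 | Age at death or at study end | No rule for earlier exit |
| 18.4, 22.1 | Death as a cause of missing non-survival outcomes; last observation carried forward; multiple imputation considered | Cannot recover uncollected deaths |

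The text between sections 8.1 and 10.0 and the consent forms were not available for review.

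**2. How often might it happen?** Section 13.3 gives six groups of 5, so 6 × 5 = 30 children and 3 × 5 = 15 per sub-type. With an assumed removal probability p per child, P(at least one of 15) = 1 − (1 − p)^15:

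| Assumed p | Expected removals | P(at least one) |
|---|---|---|
| 2% | 0.3 | 26% |
| 5% | 0.75 | 54% |
| 10% | 1.5 | 79% |
| 20% | 3 | 96% |

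**3. Effect on the infantile estimate (simulation).** From the documents: 15 children, median 47 months. Assumed:

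- Weibull survival from birth, S(t) = exp[−ln 2 · (t/47)^s], with s = 1.5 or 3.
- Entry age uniform on 6–30 months, accrual uniform over 60 months, close at 60 months.
- k children removed 3.5 months after entry, with post-entry death hazard ratio (HR) 1, 2 or 3.

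The estimator is left-truncated Kaplan-Meier, S(47) = Π(1 − d_j/n_j) over death ages up to 47 months. Here n_j counts children who have entered and are still under observation at that age. Removed children are either followed fully or censored at removal. There were 8,000 runs per cell, and ranges span both shapes.

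*Model A: the other children follow the 47-month curve and removed children do worse.*

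| k | HR | S(47), full follow-up | S(47), censored | Shift (points) |
|---|---|---|---|---|
| 1 or 3 | 1 | 0.50–0.52 | 0.50–0.52 | 0.0 to +0.1 |
| 1 | 2–3 | 0.47–0.50 | 0.50–0.52 | +1.5 to +2.4 |
| 3 | 2–3 | 0.42–0.47 | 0.49–0.51 | +4.1 to +6.9 |

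At HR 1, 0.35–0.47 of a death per removed child goes unobserved. At HR 2–3 the figure is 0.50–0.62 with k = 1. The standard deviation of S(47) under full follow-up at HR 2–3 is 16.0–18.3 points, so the shifts are about 0.1 SD (k = 1) and 0.2–0.4 SD (k = 3).

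*Model B: the whole group averages natural history and removed children are its frailer members.* The common hazard is scaled by 0.77–0.95 so that full-follow-up S(47) stays at 0.50–0.52. The chance that the observed median exceeds 47 months rises from 0.50–0.56 to 0.54–0.60 (k = 1) and from 0.49–0.56 to 0.59–0.68 (k = 3).

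*Later removal.* At 12 months after entry (Model A, HR 2–3), the shifts are +0.8 to +1.5 (k = 1) and +2.2 to +4.2 (k = 3).

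**4. Cross-check on the median (large sample).** Assume entry at 18 months, exit 6 months later for a share q, and exponential survival after entry. The hazard λ solves q·exp(−HR·29λ) + (1 − q)·exp(−29λ) = 0.5, where 29 = 47 − 18. With S₆ = q·exp(−6·HR·λ) + (1 − q)·exp(−6λ), the censored median is 18 + 6 + ln(S₆/0.5)/λ.

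Example with q = 0.1 and HR = 2: λ = 0.02222, S₆ = 0.864, and the median is 24 + 24.6 = 48.6 months, against a true 47. At HR 1 it is 47.0. At q = 0.2 it is 50.4 (HR 2) and 52.4 (HR 3).

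**The case against.** The case on the other side has substance.

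- **Exit is a late step.** Section 10.13 first looks for dietary and medication causes, then stops miglustat, then re-starts it at 50 mg. In the earlier paediatric reports in section 7.0, symptoms resolved on a lower dose or were controlled by diet. Removal may be rare, and probably later than 3.5 months. This stands, and the 12-month case shows smaller shifts.
- **The trigger is itself an adverse event, followed until it resolves.** Deaths from continuing toxicity could be captured that way, and section 19.4 requires fatal reportable events within 24 hours. With the excess hazard limited to six months after removal, the shift falls to about 0.4–1.0 points (one child) and 1.0–3.1 (three). The sign is unchanged, and deaths from the underlying disease after resolution remain outside the plan.
- **Censoring at exit is never stated.** Read literally, the endpoint requires status at study end, and keeping pre-termination data does not exclude later deaths. True, but the plan gives no means of meeting that requirement. It also names neither Kaplan-Meier nor left truncation; both are assumptions here.
- **A single clinic that keeps caring for these children will probably hear of many deaths.** Likely, but section 11.4 places part of the care with local teams, and a primary endpoint should not depend on informal knowledge.
- **The bias is smaller than sampling noise.** Correct. Unlike noise, it goes one way if removed children are at higher risk.

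**Conclusion.** The concern holds. As written, the plan requires study exit for a toxicity it expects to be common in milder form, keeps the child in the ITT survival analysis, and provides no way to learn whether the child later died.

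Bias depends on two quantities the documents do not give: how many children are removed, and how much higher their risk of death is. At average risk only information is lost. At an assumed two- to threefold hazard lasting after removal, S(47) in an infantile group of 15 rises by 1.5–2.4 points (one removed) or 4.1–6.9 points (three), and by less if removal is later or the excess is short-lived.

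Under Model A censoring does not create an apparent benefit: it hides excess deaths and returns the estimate to about the benchmark. Under Model B it makes an observed median above 47 months more likely. The defect is moderate, does not invalidate the study, and should be corrected because uncollected deaths cannot be restored at analysis.

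**What to change.** 1. In 16.2 and 21.2, and for the exits in 13.9 and 16.1, state that every ITT child who stops treatment or leaves for any reason other than withdrawal of consent is followed for vital status and date of death to study end. Use the 13.1 telephone route to families or health care providers, and state that these data enter the primary analysis.
2. In 21.2, reword the gastrointestinal bullet as permanent miglustat discontinuation, applied once the stop and re-start steps in 10.13 have failed. Follow-up is then for survival only, with no obligation to complete the remaining visits, testing or laboratory work. Keep the existing clinical follow-up of unresolved adverse events.
3. On the CRF, record the date miglustat stopped separately from the date of leaving scheduled visits.

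The cost is protocol and consent wording, one extra CRF date and occasional calls. The survival-only wording matters: without it, a retained child would stay on the full section 17.0 schedule. Calls may burden families, and contact with health care providers can limit that.

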22.0 Data Quality and Monitoring Measures

- Data Monitoring: The RDCRN DMCC identifies missing or unclear data and generates a data query to the consortium administrator contact.
- Data Delinquency Tracking: The DMCC will monitor data delinquency on an ongoing basis.

22.1 Missing data. Despite best efforts to avoid missing data, it is possible that some will occur and will be a potential limitation to the interpretation and generalizability of results. In particular, missing data may arise for non-survival outcomes (e.g. neurocognitive function data) in the event of death. For these instances, it is unclear whether a complete-case analysis (i.e. excluding patients who die) would be unbiased, and therefore would be unsatisfactory. It is also unclear what would be an appropriate magnitude of discount, to satisfactorily represent the negative outcome of death. By conducting both the complete-case analysis (unbiased if death is independent of the non-survival outcome), and an analysis with an imputed value for instances of death (intention-to-treat type of analysis), the potential magnitude of treatment effect will be better characterized.

Missing data may also arise from “lost to follow-up.” The last-observation-carried-forward imputation will be used to satisfy this type of missing data. Sensitivity analyses to evaluate the extent to which results are dependent on the approach to missing data will be conducted, wherein multiple imputations will also be considered.

23.0 Data Management

As much as possible data quality is assessed at the data entry point using intelligent online data entry via Visual Basic-designed screen forms. Data collection will initially be collected on paper forms and then subjected to checking and rescoring by the individual collecting the data. Following this, data will be entered online to the DMCC database. At the University of Minnesota, data will be entered by the individual collecting the data as well as by our research staff.

All study data will be collected via systems created in collaboration with the RDCRN DMCC and will comply with all applicable guidelines regarding patient confidentiality and data integrity.

23.1 Participant registration. Registration of participants on this protocol will employ an interactive data system in which the clinical site will attest to the participant’s eligibility as per protocol criteria and obtain appropriate informed consent. IRB approval for the protocol must be on file at the DMCC before accrual can occur from the clinical site.

The DMCC will use a system of coded identifiers to protect participant confidentiality and safety. Each participant enrolled will be assigned a local identifier by the enrollment site. This number can be a combination of the site identifier (location code) and a serial accession number. Only the registering site will have access to the linkage between this number and the personal identifier of the subject. When the participant is registered to participate in the study, using the DMCC provided web-based registration system, the system will assign a participant ID number. Thus each participant will have two codes: the local one that can be used by the registering site to obtain personal identifiers and a second code assigned by the DMCC. For all data input to the DMCC both numbers will be required to uniquely identify the subject. In this fashion, it is possible to protect against data keying errors, digit transposition or other mistakes when identifying a participant for data entry, since the numbers should match to properly identify the participant. In this fashion, no personal identifiers would be accessible to the DMCC.

23.2 Data entry. Data entry for this study will be accomplished with online electronic case report forms (CRFs). Using encrypted communication links, online forms will be developed that contain the requisite data fields.

23.3 Data quality control. As much as possible data quality is assessed at the data entry point. Data element constraints, whether independent range and/or format limitations or 'relative' referential integrity limitations, can be enforced by all methods employed for data input. QA reports assess data quality post-data entry. As we note, data quality begins with the design of the data collection forms and procedures and incorporates reasonable checks to minimize transcription and omission errors. The more important quality assurance measures are the internal validity checks for reasonableness and consistency. In addition to those described above, we propose to build these checks into the initial tables and cross tabulations that should reveal any remaining data quality issues.

23.4 Study records retention. Study records will be maintained for a minimum of two years following the conclusion of the study.

23.5 Protocol deviations. Protocol deviations for this study will be reported per local Institutional guidelines and reporting requirements.

24.0 Human Subjects

24.1 GCP statement. This clinical trial will be conducted in accordance with the ethical principles that have their origin in the Declaration of Helsinki, and that are consistent with Good Clinical Practice and all applicable regulatory requirements.

24.2 Risks. The potential risks of this study are:

By participating in this study the subjects will run a slight risk of loss of privacy. The research team will make every effort to protect the subjects by making all of the data that the research team will take from the subjects' records anonymous by identifying it only with a number. Researchers will remove information such as name, address, and phone number, and replace that information with a code number. Only the research investigators will be able to identify which data belong to a given subject; thus the risk is minimal.

None of the neuropsychological tests are in any way harmful for participants, although they may be fatiguing. No embarrassing questions or sensitive stimuli will be used in the neuropsychological testing.

24.3 Benefits. Studies of miglustat in infantile, juvenile and adult gangliosidoses have demonstrated safety, but do not show significant clinical improvement.²³⁻²⁵ At the University of Minnesota, neuropsychiatric evaluations have shown improvement in some assessed domains for gangliosidosis patients using the goal miglustat dose and the ketogenic diet. Seizure frequency and severity have improved in all the patients; preliminary results suggest further improvement may be possible with the combination of miglustat and the ketogenic diet.

The ketogenic diet may provide benefits for patients with gangliosidoses by the following mechanisms:

- 1) Minimize or reduce the severity of food-drug interactions between miglustat and carbohydrates

- 2) Reduce seizure activity
- 3) Increase the bioavailability of miglustat to the central nervous system.

24.4 Recruitment. Patient recruitment is limited by availability of such patients. All individuals with these disorders will be considered. Disorders may be unevenly prevalent in Ashkenazi Jews, French Canadians, Louisiana Cajuns, and certain old-order Amish. All ethnic and racial groups will be recruited.

24.5 Written and informed consent. Written informed consent will be obtained from each participant before the subject undergoes any study-specific procedures or assessments and after the aims, methods, anticipated benefits, and potential hazards are explained. The participant's willingness to participate in the study will be documented in writing in a consent form, which will be signed by the participant with the date of that signature indicated. The investigator will keep the original consent forms and signed copies will be given to the participants. It will also be explained to the participants that they are free to refuse entry into the study and free to withdraw from the study at any time without prejudice to future treatment. Written and/or oral information about the study in a language understandable by the participant will be given to all participants.

24.6 Process of consent. At the University of Minnesota the following (from our IRB) will be explained to the patient by an approved member of the research team: consent and assent forms will be given to potential participants prior to enrollment so that they have ample time to review the information and ask questions about the study. Forms can be mailed to the individuals in advance of their participation so that they can read and ask any questions before considering participating. Investigators will ensure that the participant or their legally authorized representative understand the information provided and obtain informed consent. The consenting process will be thoroughly documented in the participants' research charts.

24.7 Certificate of Confidentiality. To help protect participant privacy, a Letter of Confidentiality has been obtained from the National Institutes of Health (NIH). With this Certificate, the researchers cannot be forced to disclose information that may identify a study participant, even by a court subpoena, in any federal, state, or local civil, criminal, administrative, legislative, or other proceedings. The researchers will use the Certificate to resist any demands for information that would identify a participant, except as explained below.

The Certificate cannot be used to resist a demand for information from personnel of the United States Government that is used for auditing or evaluation of Federally funded projects or for information that must be disclosed in order to meet the requirements of the federal Food and Drug Administration (FDA).

Even with the Certificate of Confidentiality, the investigators continue to have ethical obligations to report child abuse or neglect and to prevent an individual from carrying out any threats to do serious harm to themselves or others. If keeping information private would immediately put the study participant or someone else in danger, the investigators would release information to protect the participant or another person.

Department of Health and Human Services (DHHS) personnel may request identifying information for purposes of performing audits, carrying out investigations of DHHS grant recipients, or evaluating DHHS funded research projects.

